**11. Multi-site Study Management****11.1. Is this a multi-site study?**

No Yes: If yes; describe plans for communication among sites regarding adverse events, interim results, protocol modifications, monitoring of data, etc.

The NFP program has a long-standing, centralized National Service Office that oversees communication with NFP implementing agencies. The study team has regular communication with the National Service Office, and will keep them abreast throughout the study period of any adverse events, interim results, or protocol modifications that should be shared with NFP implementing agencies. In consultation with the National Service Office, the study team will determine the best way to communicate these updates to the NFP implementing agencies, depending on the content and urgency of the message (e.g. via email, phone, etc.).

12. Investigational Drug/Biologic/Device**12.1. Does this study involve an Investigational Drug/Biologic/Device?**

No: If no; skip to 13.1

Yes: If yes; identify and describe the drug/biologic/device (e.g., marketing status: Is there an IND/IDE, classification of a device as significant vs. non-significant risk)

12.2. Describe its administration or use**12.3. Compare the research drug/biologic/device to the local standard of care****12.4. Describe plans for receiving, storage, dispensing and return (to ensure that they will be used only for participants and only by authorized investigators)****12.5. If proven beneficial, describe anticipated availability and cost to participants post-study; plans (if applicable) to make available****13. HIPAA Privacy Protections****13.1. Are HIPAA privacy protections required? Please note that only Harvard University Health Services and Harvard School of Dental Medicine are covered entities at Harvard. Harvard is otherwise not a HIPAA covered entity. If, however, data is derived from a Covered Entity (e.g. a hospital or community health center), mark 'yes' and address the items below.**

No: If no; skip to 14.1

Yes: If yes; include at least one of the following:

Describe plans for obtaining authorization to access protected health information

Provide the rationale for a waiver of authorization or limited waiver of authorization request

We used Harvard's approved template for 'Consent at HIPAA covered entities.' This template provides clear language about"

- The privacy rules of the HIPAA law, including a definition of PHI, and participants' rights under the law
- Who will be able to see the PHI for research purposes
- What types of PHI will be collected
- Where the PHI will be collected from
- How the PHI will be protected to maintain each participant's privacy and confidentiality
- How the PHI will be used

The consent form and the NFP staff who will be conducting the informed consent process will make it clear to the participant that by signing the consent form, she is authorizing the study team to use her and her children's PHI. The participant will also be informed that she may cancel this authorization at any time by contacting the study team, in writing, at the address on the consent form. If she decides not to authorize the investigators to use her PHI or she cancels this authorization, she and her children will no longer be able to participate in this research study, and the use or sharing of future PHI will be stopped. However, the PHI that has already been collected may still be used.

14. Data and Specimen Banking

14.1. Does the study include Data and Specimen Banking?

No: If no; skip to 15.1

Yes: If yes; identify what will be collected and stored, and what information will be associated with the specimens

14.2. Describe where and how long the data/specimens will be stored and whether participants' permission will be obtained to use the data/specimens in other future research projects

14.3. Identify who may access data/specimens and how

14.4. Will specimens and/or data be sent to research collaborators outside of Harvard?

No Yes: If yes; describe the plan

20.5 Will specimens and/or data be received from collaborators outside of Harvard?

No Yes: If yes; describe the plan

15. Sharing Study Results

15.1. Is there a plan to share study results with individual participants?

No Yes: If yes; describe the plan

15.2. Is there a plan to disseminate aggregate results to the community where the research is conducted?

No Yes: If yes; describe the plan

Results from the study will be disseminated to academics, the public, and the policy community. The study can provide state and federal policy-makers much needed information about the effect of expanding or implementing home visiting programs, taxpayers and voters information about the use of public resources to subsidize such programs, and participants information about the efficacy of such interventions.

16. Regulatory Compliance

16.1. Describe plan for monitoring regulatory compliance, in order to ensure proper record keeping and retention of required regulatory documents

The software (SurveyCTO) will time and date stamp the recording of informed consent, the baseline survey, and the randomization. The study team will monitor the data from this in real time to ensure that protocol is followed (including that consent, survey, and randomization were done in the proper order) and that the clients, the field offices, and the recruiters did not tamper with the randomization. Additionally, we will work with NFP administrators to ensure the overall fidelity of the implementation to the evaluation plan through random back checks, site visits, and monitoring of other data.

The PI will make sure that all investigators and study staff have up-to-date Human Research Training certificates on file. The PI will also ensure that her CV, as well as the CVs of the other co-investigators, have been updated within the past 2 years, and that they are signed and dated and centrally stored.

The study team will also keep any grant progress reports, correspondence to and from funding agencies, signed agreements/contracts, external IRB approvals, and a roster of members with documentation of HSPH's Federalwide Assurance (FWA) Number on file throughout the course of the study.

## **Pre-Analysis Plan: Impact of Nurse-Family Partnership on Maternal and Early Child Outcomes**

*Note: This is version 2 of the pre-analysis plan reflecting plans for study design as of January 20, 2021.*

A full study protocol describing study motivation, design, and plans for analysis has been published in McConnell et al. (2020). We do not repeat those materials here. In this pre-analysis plan, we provide more detail about our planned analytical choices including analytic details for defining primary and secondary outcomes for the three domains of analysis defined in the study protocol in Addendums 1-3. This analysis plan will be updated as analytical plans for additional longitudinal outcomes are developed.

### **1. Methods**

While other methods are outlined in the study protocol, in this pre-analysis plan we provide further details on methods related to sample construction and analytical plans.

#### **A. Sample construction**

##### **A.1. Tracking study moms and babies**

All study outcomes will be measured using administrative data sources, which require matching to state administrative records. Because we plan to analyze outcomes for both the mother and child, we define several relevant samples for analysis of outcomes for the mother-child dyad. For most analyses, we will want to consider the sample of mother-baby dyads where a live birth occurred from the pregnancy in gestation at the time of enrollment. We call this the index birth. Mother-baby dyads who experience an index birth will be the primary sample for longitudinal analyses examining the impact of the program. As the mother is the unit of randomization and we expect multiple births to be rare, we plan to aggregate outcomes pertaining to children resulting from the index birth to the mother level. To identify the index birth, we first match the mother to a birth certificate in vital records. If the date of birth on the birth certificate is within 120 days before or after the estimated delivery date as reported on the baseline survey, we will consider the birth to be related to the pregnancy that was in gestation at the time of study enrollment. Births that occur outside of this window will not be included in the sample of index births.

We may also analyze outcomes for the broader sample of mothers with at least one matched administrative record related to the pregnancy reported at the time of enrollment. We will call this the index pregnancy. We define the index pregnancy as follows: when there is a matched index birth or fetal death in vital records, we define the pregnancy period as the period

---

 Specified in McConnell et al. (2020) as a death of the fetus occurring at or after 20 weeks of gestation.

covering the weeks of gestation provided in the obstetric estimate on the vital record until the date of birth or fetal death. In the absence of an index birth or fetal death, we define the pregnancy period as the period covering 42 weeks prior to the expected delivery date provided on the baseline survey. We will consider a mother to be matched to the index pregnancy if she has any matched administrative records pertaining to the index pregnancy (including antenatal care, probable pregnancy loss or birth related records from Medicaid claims or hospital discharge or evidence of a birth or fetal death from vital records). Table 1 summarizes the definitions and data sources used to identify index pregnancies and live index births.

When tracking children in the study, we will define two key periods. We anticipate that the children of most mothers who enroll in the trial will be eligible for Medicaid for their entire first year of life, as the income requirements for infants are similar to those of pregnant women. However, as summarized in Table 2, in some years of the study, income requirements became more restrictive after the first year of the child's life. Furthermore, families whose children remain income-eligible into their child's second year of life must submit an annual review form to retain coverage. Therefore, we plan to measure outcomes for children resulting from index births in the study to two critical time points: through their first 12 months of life and through their first 24 months of life.

Table 1. Sample Tracking Definitions

Sample tracking measure	Data Source(s)	Definition
Index pregnancy	Birth Certificates, fetal death records, Medicaid claims and eligibility, hospital discharge	Having matched administrative records for one or more of the outcomes listed below during the period of the index pregnancy. This period is defined as covering the weeks of gestation provided in the obstetric estimate on the vital record until the date of birth or fetal death, when a mother has a matched index birth or fetal death record. In the absence of an index birth or fetal death, we define the pregnancy period as the time covering 42 weeks prior to the expected delivery date provided on the baseline survey.

		
 
• A live birth certificate for the index birth,
 
• A Kuklina identified live birth in Medicaid claims or hospital discharge records occurring within 120 days of the expected delivery date
 
• A probable pregnancy loss in Medicaid claims or hospital discharge occurring during the index pregnancy
 
• A fetal death record in Vital Records occurring during the index pregnancy
 
• An antenatal care visit in Medicaid claims occurring during the index pregnancy
 
• Enrollment in Medicaid for pregnant women overlapping with the index pregnancy period
 

Index birth	Baseline survey, birth certificates	A birth identified by a matched birth certificate in Vital Records with a date of birth within 120 days before or after the estimated delivery date reported on the baseline survey.

Table 2. South Carolina Medicaid income eligibility criteria as a percent of the Federal Poverty Line over the study period

	Jan 2016	Jan 2017	Jan 2018	Jan 2019	Jan 2020	Jan 2021
Pregnant women 	199%	199%	199%	199%	199%	194%
Parents 	67%	67%	67%	67%	67%	95%
Children 0-1 	213%	213%	213%	213%	194%	208%
Children 1-5 	213%	213%	213%	213%	143%	208%
Children 6-18 	213%	213%	213%	213%	133%	208%

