#### **1.1. Defining the Sample for Analysis**

For analysis of our primary adverse birth outcome, we will consider our primary sample to be mothers who experience either a fetal death or index birth (defined in section A.1 of the pre-analysis plan). For analysis of other outcomes, our primary sample will be mothers with an index birth, as many outcomes will not be observable in the case of fetal death.

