##### **1.2.1 Primary Outcome**

Our primary outcome for this domain is an adverse birth outcome, which we define as having a preterm birth (less than 37 weeks' gestation), a newborn being small for gestational age (less than 10th percentile of US births conditional on gestational age), having low-birth weight (less than 2500 grams), or experiencing perinatal mortality (fetal death occurring at or after 20 weeks' gestation or mortality in the first 7 days of life). Data for the adverse birth outcome will come from South Carolina birth records, death records, and fetal death records.

For mothers with multiple births, we define the outcome based on having an adverse birth outcome for any child from the index pregnancy. While preterm birth and other adverse birth outcomes may be more common among multiple births, we anticipate that rates of multiple births will be equal across treatment and control arms. We may also explore alternative specifications of this outcome that include only singleton births.

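### The ±120-day index-birth window drops live births at 20w0d–22w5d while fetal deaths count from 20 weeks, and it can admit births from a later pregnancy

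*SAP*

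**What the plan says.** SAP A.1 sets the aim: the index birth is the live birth that results from the pregnancy the mother was carrying when she enrolled. The working rule is a calendar test. A matched birth certificate qualifies if its date falls "within 120 days before or after the estimated delivery date as reported on the baseline survey", and "Births that occur outside of this window will not be included in the sample of index births". SAP Table 1 repeats the rule.

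Fetal deaths follow a different rule. The footnote to A.1 defines one as "a death of the fetus occurring at or after 20 weeks of gestation", and Table 1 asks only for "A fetal death record in Vital Records occurring during the index pregnancy", with no 120-day limit.

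Addendum 1, section 1.1, makes the primary sample for the adverse birth outcome "mothers who experience either a fetal death or index birth". Section 1.2.1 counts preterm birth (under 37 weeks), small for gestational age, low birth weight, or perinatal mortality, the last being "fetal death occurring at or after 20 weeks' gestation or mortality in the first 7 days of life". It sets no lower gestational limit for live births.

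For births seen only in claims or discharge data, Table 1 and Addendum 1, section 1.4, apply the same 120 days. The probable-loss category in section 1.4 applies only when no certificate has already matched as the index birth.

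Protocol 4.4 admits women at any gestation below 28 weeks and describes the due date as a best guess.

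**The concern.** At the early end, two mothers who deliver at the same gestation are treated differently according to whether the baby shows signs of life, an event after randomization. The excluded mother would have counted as an event, so the exclusion depends on the outcome itself. She also leaves the child-health and birth-spacing samples (Addendum 2, 2.1; Addendum 3, 3.1).

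At the late end, a woman who loses the enrolled pregnancy early and soon conceives again can enter the birth, child-health and birth-spacing analyses with a child conceived after enrollment. Her entry depends on rapid repeat conception, which bears directly on the birth-spacing outcome that the program is meant to change.

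**Working it through.** **1. The SAP's own figure from the window.** Addendum 3, section 3.3, gives the last due date as 7 November 2020. Adding 120 days gives 7 March 2021; the SAP prints 7 March 2020. Day and month agree, so the plan does use the full 120 days. The year is a separate slip and does not affect this point. From 7 March 2021, adding 24, then 6, then 3 months gives 7 March 2023, 7 September 2023 and 7 December 2023; the last two are as printed.

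**2. Window limits in gestational days.** Assumption: due date = 280 days (40w0d).
- Lower: 280 − 120 = 160 days = 22w6d.
- Upper: 280 + 120 = 400 days = 57w1d.
- Fetal-death threshold: 20 × 7 = 140 days. Gap: 160 − 140 = 20 days, i.e. 20w0d to 22w5d.

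**3. Sensitivity to the 280-day assumption.**

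| True gestation at the reported due date | Lower limit | Upper limit | Gap above 20w0d |
|---|---|---|---|
| 39w0d | 21w6d | 56w1d | 13 days |
| 40w0d | 22w6d | 57w1d | 20 days |
| 41w0d | 23w6d | 58w1d | 27 days |
| 42w0d | 24w6d | 59w1d | 34 days |

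The gap does not close anywhere in this range.

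**4. Two deliveries at 21w0d (day 147).** A fetal death is past 140 days, so it is in the sample and is an event. A live birth is 280 − 147 = 133 days before the due date, so it is outside the window and out of the sample. It would have been an event, because day 147 is before day 259 (37w0d).

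**5. Does another rule recover her?** The robustness sample in Addendum 1, section 1.5, adds births from claims and discharge data, but Table 1 and section 1.4 hold those to the same 120 days. None of the three attrition categories in section 1.4 clearly fits: a linking error needs a record inside the window, and the unmatched category needs no birth record at all.

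**6. Late end.** Assume the new pregnancy's start (last-menstrual-period equivalent) is the day of loss, which is the fastest case. On the original clock, a 40-week birth then falls at:
- loss at 6w: 6 + 40 = 46w0d, admitted
- loss at 12w: 52w0d, admitted
- loss at 17w: 57w0d, admitted
- loss at 18w: 58w0d, not admitted

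The probable-loss category cannot override this, because a certificate has already matched. A.1 then takes the pregnancy period from that certificate's obstetric estimate, so the earlier loss can fall outside the index pregnancy. For a birth at 57w1d to be the enrolled pregnancy delivered at 40–42 weeks, the due date would have to be wrong by 17w1d to 15w1d (400 − 280 = 120 days; 400 − 294 = 106 days).

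**7. Size.** Addendum 4, Table 3, gives 3,295 + 1,637 = 4,932 mothers with an index birth. The rate of live births at 20w0d–22w5d is not in the documents. At an assumed 0.05%, 0.1% and 0.3%, the counts are 2.5, 4.9 and 14.8.
- Against the composite: Protocol 5.2 assumes 12% preterm, and 0.12 × 4,932 = 592. The missing births are 0.05/12 = 0.4% to 0.3/12 = 2.5% of that, and a smaller share of the wider composite.
- Against perinatal mortality: at an assumed 1–1.5%, there are 49–74 deaths. Here 2–15 missing births could matter if most die within 7 days.

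The documents give no input from which to size the late end.

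**The case against.** The strongest defense is that the due date is a guess, so a wide window is sensible tolerance for misdating. That stands in part. A reader might infer that every birth well past term on the baseline clock belongs to a new pregnancy. The documents do not support this: at 44–46 weeks a misdated index birth is plausible, and only toward the upper limit does the required dating error become hard to credit. Protocol 4.7 does foresee women further along than they reported, but such women deliver before the reported due date. That supports tolerance on the early side, and it also raises the effective floor (step 3).

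Size is the second objection, and it stands. A reader might also infer that up to 30% of perinatal deaths are lost. That figure appears only by setting the highest assumed loss against the lowest assumed death rate (15/49), and neither rate is in the documents. Women enrolled after 22w5d cannot deliver in the gap, so applying a rate to all 4,932 may overstate the count. Perinatal mortality alone is a secondary outcome.

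Third, Addendum 4 (February 2025) describes manuscripts on trial results, birth outcomes among them, as published or forthcoming. Replacing the pre-specified sample now would be a change made after results were known. This stands and governs the order of the fix.

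Last, the SAP leaves other methods to a published protocol paper that is not among the documents, so a safeguard there cannot be ruled out. The SAP does, however, present A.1 as its detailed account of sample construction.

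**Conclusion.** The point holds as a definitional inconsistency. The calendar window does not implement the SAP's own description of an index birth, and no rule in the documents repairs either end. The early exclusion is certain from the wording, given a due date near 280 days; the late inclusion is possible but cannot be counted. The early end is probably 2–15 mothers under the assumed rates: small for the primary composite, possibly material for perinatal mortality.

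Two stronger conclusions are not supported. One is that the treatment comparison is biased: no difference by arm is shown, and the by-arm reporting of missing outcomes in Addendum 1, section 1.4, may reveal some imbalance, although it does not repair the definition. The other is that the birth-spacing interval starts from the wrong child. After a loss before 20 weeks there is no other index child and no countable fetal death; the fault is that the woman is included at all. Competing start dates arise only if a fetal death at 20 weeks or later is followed by a birth inside the window, for which the SAP gives no tie-break.

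**What to change.** Define an index birth as a live birth that meets all three conditions:
- gestation of 20 weeks or more by the obstetric estimate on the vital record;
- date of birth on or after the baseline survey date;
- implied pregnancy start (date of birth minus gestation) before the survey date.

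Use the 120-day window only where the obstetric estimate is missing. The second condition keeps out an earlier undisclosed birth; the third keeps misdated true index births and removes later conceptions. Widening the window to ±140 days is no substitute: it would close the early gap but move the upper limit to 60w0d.

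For results already reported, keep the pre-specified sample. Report by arm how many births are reclassified at each end, and re-run the adverse-birth, perinatal-mortality and birth-spacing outcomes under the new rule as a sensitivity analysis. Use the new rule as the main definition for analyses not yet done.

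The cost is one re-run of the match and a small change in sample counts. No new data are needed, since A.1 and the antenatal-care section of Addendum 1 already use the obstetric estimate.

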### Antenatal Care Utilization & Quality

Analyses of outcomes related to antenatal care utilization and quality is planned as a stand-alone analysis. We will examine three groups of outcomes related to antenatal care utilization and quality: utilization of health care services during pregnancy, guideline-recommended antenatal care, and indicators related to antenatal health. We list the outcomes that fall under each area, and their associated data sources, below. We also include the CPT/HCPCS, NDC (National Drug Code) and ICD-10 codes used to identify the outcomes that use Medicaid claims or hospital discharge data in Table 1.3.

The primary sample for this analysis will be mothers with an index birth. We will use vital records, hospital discharge, and Medicaid claims data for the analyses. Mothers who do not match to one of these data sources will not be included in the sample for the corresponding outcomes (e.g., mothers who do not match to Medicaid claims will not be included in the analyses of guideline-recommended antenatal care).

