#### Guideline recommended antenatal care

- Anatomy scan (between 18-22 weeks' gestation) [Medicaid claims data]
- Gestational diabetes test (between 24-28 weeks' gestation) [Medicaid claims data]
- TDAP vaccine (between 27-36 weeks' gestation) [Medicaid claims data]
- Group B strep test (between 35-38 weeks' gestation) [Medicaid claims data]

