#### Antenatal health

- Smoking cessation during pregnancy [vital records data]
  - We will consider an enrollee to have ceased smoking during pregnancy if their vital record indicates that they smoked pre-pregnancy and that they did not smoke during pregnancy.
- Recommended gestational weight gain [vital records data]
  - Gestational weight gain will be classified as “recommended” if it is within the guidelines published by the National Academy of Medicine (formerly the Institute of Medicine).

The guideline-recommended antenatal care services should be received at the appropriate gestational age during the pregnancy. The gestational age at the time of the test will be calculated as the date of the test minus the approximate date of last menstrual period (in days). We will approximate the enrollee's date of last menstrual period using the child's date of birth and obstetrician's estimate of gestational age at delivery from the vital records. If these fields are missing, we will define the approximate date of last menstrual period as the beginning date of the index pregnancy (defined above).

Each of these outcomes can only be measured among pregnancies that reach the gestational age at which the care is recommended. The main analyses will only include pregnancies that last at least as long as the gestational age recommended for each outcome. However, it is possible that NFP has a direct effect on gestational age, which would mean that the sample of mothers observed could differ across treatment and control arms. If that is the case (i.e., if gestational age at birth between treatment and control group is statistically significantly different), then we will conduct a bounding exercise as a robustness check for the guideline-concordant care outcomes. Using Group B Strep as an example, the main analysis will compute the average treatment effect (ATE) among people whose pregnancies last at least 35 weeks. If gestational age is statistically significantly different between control and treatment arms, we will estimate two bounds on this ATE: (1) a recalculated ATE assuming *all* people who

did not reach 35 weeks' gestation would have received the test, and (2) a recalculated ATE assuming *none* of the people who did not reach 35 weeks' gestation would have received the test.

Table 1.3. Codes for analyses of antenatal care utilization and quality

	CPT/HCPCS	NDC	ICD-10

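### When the obstetric estimate is missing, the SAP's only usable last menstrual period is the due date minus 42 weeks, which under standard 40-week dating makes gestational age at each timed antenatal test 14 days too high

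*SAP*

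**What the plan says.** SAP A.1, repeated in Table 1, gives two definitions of the index pregnancy period. If an index birth or fetal death is matched in vital records, the period is built from the obstetric estimate on that record and runs to the birth or fetal death. If neither is found there, the SAP falls back on "the period covering 42 weeks prior to the expected delivery date provided on the baseline survey". That second period starts at the due date minus 42 weeks and ends at the due date.

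Addendum 1, under Antenatal health, dates each guideline-recommended test by subtracting an approximate LMP from the test date. The LMP is normally derived "using the child's date of birth and obstetrician's estimate of gestational age at delivery from the vital records". If those fields are missing, "we will define the approximate date of last menstrual period as the beginning date of the index pregnancy", with a pointer back to the earlier definition.

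The test windows, listed under Guideline recommended antenatal care, are:
- anatomy scan: 18-22 weeks
- gestational diabetes test: 24-28 weeks
- TDAP: 27-36 weeks
- group B strep test: 35-38 weeks

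On who is analysed, the antenatal care section says: "The primary sample for this analysis will be mothers with an index birth". Addendum 1, section 1.7, combines the four services into one index, the proportion received.

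**The concern.** A period used to search for records can start generously early. An LMP cannot, because any error in it passes one for one into every gestational age computed from it. The SAP makes one date serve both purposes, and no section corrects for this.

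The four services count only if they fall inside a gestational window. For a woman on the fallback, a test done on time late in its window would be scored as too late, and a test done up to two weeks early would be scored as on time. The individual service outcomes and the summary index would carry that misclassification. Addendum 4 (Table 4) lists the same four services among the prenatal outcomes for its heterogeneity analysis.

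**Working it through.** **Inputs**
- Fallback period: 42 weeks ending at the baseline-survey due date (SAP A.1, Table 1). 42 × 7 = 294 days.
- Gestational age at test = test date − LMP (Addendum 1, Antenatal health).
- Test windows: as listed above.
- LMP-to-due-date interval: 40 weeks, 40 × 7 = 280 days. This is an assumption (standard obstetric dating), because the documents do not give the interval.

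**Which start date the fallback can use.** A mother in the antenatal sample has an index birth, so by definition she has a matched birth certificate with a date of birth. The only dating field that can be missing is the obstetric estimate. The vital-record definition in A.1 needs that estimate, so it cannot supply a start. The due date minus 42 weeks is the only definition left that can be computed.

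**Size of the shift**

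Fallback age − true age = [test date − (due date − 294)] − [test date − (due date − 280)] = 294 − 280 = 14 days.

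A woman at her due date would be scored as 42 weeks 0 days. For the latest expected delivery date in SAP 3.3, 7 November 2020, the fallback LMP is 18 January 2020. Under 40-week dating it is 1 February 2020.

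If the assumed interval is varied, the shift is 42 minus that interval: +3 weeks for 39, +2 for 40, +1 for 41, and none only for 42.

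**Effect on the windows** (true window = stated window − 2 weeks; share covered = overlap ÷ stated width)

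| Service | Stated | True weeks captured | Share of stated window covered |
|---|---|---|---|
| Anatomy scan | 18-22 | 16-20 | 2/4 = 50% |
| Diabetes test | 24-28 | 22-26 | 2/4 = 50% |
| TDAP | 27-36 | 25-34 | 7/9 = 78% |
| Group B strep | 35-38 | 33-36 | 1/3 = 33% |

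If the closing week counts in full, the shares are 3/5 = 60%, 3/5 = 60%, 8/10 = 80% and 2/4 = 50%. All of these are shares of window width. They are not shares of tests, since the documents do not say when tests fall within a window.

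The main analysis keeps only pregnancies that reached the recommended age. If the same LMP sets gestational length, the 35-week restriction for group B strep admits pregnancies of true 35 − 2 = 33 weeks.

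**Reach.** The documents give no rate of missing obstetric estimates. Addendum 4, Table 3 shows 3,295 + 1,637 = 4,932 mothers with an index birth. Illustrative rates of 0.5%, 1%, 5% and 10% would mean about 25, 49, 247 and 493 women on the fallback.

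**The case against.** The strongest reply is that the two rules hardly meet. A.1 reserves the 42-week definition for women without an index birth or fetal death, while the guideline-care sample is mothers with an index birth. On that reading the SAP never tells anyone to use the due date minus 42 weeks for these mothers. This is fair as a reading, but it leaves a mother without an obstetric estimate with no LMP at all, so the text still needs the same correction. The reply is also right that the main LMP rule is sound, that the same rule applies in both arms, and that the affected group is probably small.

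A reader might infer more than the documents support:
- *That every woman without a vital record is misdated.* She is outside the guideline-care sample. Births found only in claims or discharge data are dated by the Z3A code, or otherwise from the admission date and due date (Addendum 1, section 1.5.1), not from the 42-week start.
- *That late fetal deaths are lost because the period stops at the due date.* A fetal death in vital records sets its own end date. Fetal deaths found in claims have no stated due-date cut-off (section 1.5.1), and claims-identified live births have their own 120-day window (Table 1). Antenatal visits after the due date do fall outside the fallback period, but one earlier record is enough to match a woman to the pregnancy.
- *That about half of on-time tests are misclassified.* The loss differs by service, TDAP has a nine-week window, and the figures describe window width only.
- *That a 42-week look-back is itself an error.* As a search window it is merely generous. The fault lies in using its start as an LMP.

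**Conclusion.** The point stands with limited reach. Under the 40-week assumption, the only computable fallback LMP makes gestational age 14 days too high and moves all four timed-care windows two weeks earlier in true gestation. On the strict reading, the fallback is undefined instead.

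The effect is confined to index-birth mothers whose certificate lacks the obstetric estimate, the four timed antenatal services and their summary index. The misclassification is the same in both arms unless missing estimates differ by arm. A reader might fear for the primary results, but they do not depend on this rule: the adverse birth outcome is dated from vital records, its claims-based check follows section 1.5.1, and neither child injury nor birth spacing uses the fallback LMP.

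**What to change.** In Addendum 1 (Antenatal health), define the fallback LMP as the baseline-survey due date minus 280 days, and state that it is separate from the 42-week record-search period in A.1. Say explicitly that it applies to a mother with an index birth whose obstetric estimate is missing. Check that the code for test timing, and for whether a pregnancy reached the recommended age, uses this date. Report by arm how many women were dated by the fallback.

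Extending the search period past the due date is optional, and nothing in this point depends on it.

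The cost is one constant and a sentence or two in the SAP, a code check, and one line in a table. If the antenatal outcomes have already been derived, the affected women can be counted and those outcomes rerun. Addendum 4 says its own analyses had not been performed when it was submitted, so the correction should be in place before those outcomes are reused there.
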